3.2. Eligibility Criteria for Subject Selection

3.2.1. Inclusion Criteria

In order to be eligible to participate in the study, subjects must meet all of the following inclusion criteria:

1. Be adequately informed and understand the nature and risks of the study and be able to provide consent.
2. Be undergoing planned elective abdominoplasty.
3. Be willing to have their tissue donated for evaluation.
4. Be female and ≥ 18 years of age and ≤ 55 years of age at time of informed consent.
5. Have a body mass index (BMI) between ≥ 20.0 and $\leq 35.0 \text{ kg/m}^2$.
6. Be willing to apply sunscreen to the abdomen before each exposure to the sun while participating in the study (ie, Screening through Day 28 End of Study [EOS]/Early Termination [ET] Visit).
7. Be judged to be in good health, based upon the results of a medical history, physical examination, and any standard of care laboratory profile available at Screening.
8. Be postmenopausal (of nonchildbearing potential) with no history of menstrual flow in the 12 months prior to the Screening Visit; or, if of childbearing potential, be nonpregnant, nonlactating and agree to use effective contraception when with a male partner for the duration of the study. Acceptable forms of contraception include hormonal measures (oral contraceptive pills, contraceptive patch, contraceptive ring, or injections), intrauterine devices, double barrier method (condom plus diaphragm, condom or diaphragm plus spermicidal gel or foam), surgical sterilization of the male partner, and abstinence.
9. Have a negative serum pregnancy test at screening and a negative urine pregnancy prior to the first dose of study drug.
10. Be willing and able to cooperate with the requirements of the study.

3.2.2. Exclusion Criteria

In order to be eligible to participate in the study, subjects must not meet any of the following exclusion criteria:

1. Is from a vulnerable population, as defined by the US Code of Federal Regulations (CFR) Title 45, Part 46, Section 46.111(b) and other local and national regulations, including but not limited to, employees (temporary, part-time, full time, etc) or a family member of the research staff conducting the study, or of the sponsor, or of the contract research organization, or of the Institutional Review Board (IRB)/Independent Ethics Committee (IEC).
2. Has any of the following systemic conditions:
 - a. Coagulation disorder.

- b. Evidence or history of malignancy (other than excised basal-cell carcinoma) unless there has been no recurrence in at least 5 years.
- c. History of keloidal scarring or abnormal wound healing.
- d. Concurrent diseases or conditions that might interfere with the conduct of the study, confound the interpretation of the study results, or endanger the subject's well-being. Any questions about concurrent diseases should be discussed with the Sponsor Medical Monitor.
- e. Evidence of clinically significant abnormalities observed/recorded on physical examination, vital signs, clinical laboratory values at screening and/or during presurgery preparation at site (including electrocardiogram [ECG], laboratory, etc).

3. Has any of the following local conditions in the areas to be treated:

- a. History of lower extremity thrombosis or post-thrombosis syndrome.
- b. Vascular disorder (eg, telangiectasia) in area to be treated.
- c. Inflammation or active infection.
- d. Active cutaneous alteration including rash, eczema, psoriasis, or skin cancer within last 5 years.
- e. Has a tattoo and/or a mole located within 2 cm of the site of injection.

4. Requires the following concomitant medications before or during participation in the trial:

- a. Anticoagulant or antiplatelet medication or has received anticoagulant or antiplatelet medication 7 days prior to injection with study drug (CCH) (except for ≤ 150 mg aspirin daily, permitted only within a window-specific time frame as determined by the investigator prior to abdominoplasty surgery).

5. Has history of any abdominal surgery, including but not limited to liposuction, caesarean section, appendectomy, cholecystectomy, or umbilical hernia repair.

6. Has used any of the following within the timelines as identified below OR has used/intends to use any of the following:

- a. Injections (eg. mesotherapy), radiofrequency device treatments, laser treatment cryolipolysis, or surgery (including subcision and/or powered subcision) within the abdominal area during the 18-month period before injection of study drug.
- b. Any investigational treatment in the abdominal area during the 12-month period before injection of study drug.
- c. CoolSculpting® or similar treatments of the abdomen during the 18-month period before injection of study drug.
- d. Deep massage therapy (such as Endermologie™) or similar therapy, within the abdominal area during the 6-month period before injection of study drug.
- e. Creams (eg, Celluvera™, TriLastin®) and/or home therapies within the abdominal area during the 2-week period before injection of study drug and at any time during the course of the study.

- f. Bath/shower salts or sugar/salt scrubs, lotions, loofahs, or other exfoliating products on the abdominal area during the 2-week period prior to injection of study drug and at any time during the course of the study.
- 7. Is presently nursing or providing breast milk in any manner.
- 8. Intends to become pregnant during the study.
- 9. Intends to initiate an intensive sport or exercise program regimen during the study.
- 10. Intends to use any tanning spray or tanning booths during the study.
- 11. Has received any investigational drug or treatment within 30 days prior to first injection of study drug.
- 12. Has a known systemic allergy to collagenase or any other excipient of study drug.
- 13. Has received any collagenase treatment at any time prior to treatment in this study.
- 14. Has a medical history of being treated with (or received) CCH or XIAFLEX®.
- 15. Has been known to have syncope.
- 16. Any other condition(s) that, in the investigator's opinion, might indicate the subject to be unsuitable for the study.

3.3. Selecting and Marking Treatment Area

For each subject, there will be 2 marked areas (Area 1 and Area 2) of the abdomen selected for injection with CCH plus a marked non-injected control area for comparison. The control area will be located between the two treatment areas. Treatment areas of each subject group will be marked as Treatment Area 1 and Treatment Area 2 respectively with the non-injected area marked as control.

At each dosing visit, the treatment areas of each selected subject will be photographed **after marking the treatment area and the injection site with a surgical marker and a temporary tattoo (but prior to CCH dosing or the abdominoplasty procedure)**, while the subject is in a consistent, standardized relaxed standing pose. On Day of Surgery (Day 0), prior to abdominoplasty procedure, the borders of the treatment area will be marked with a surgical marker. Following marking, the treatment areas will then be photographed while the subject is in a standing pose.

3.4. Study Drug Administration

Subjects who qualify for the study will be given a maximum total dose of approximately 0.21 mg CCH over the course of the study, which will be administered as 3 doses of 0.07 mg CCH each, approximately, during 2 or 3 dosing sessions.

The dosing detail, volume and concentration is explained in [Table 2](#) below.

Table 2: Study Treatment (All Subjects)

Group	Injection Technique	Dose per Each Administration	Volume per Each Dose	Number of Doses	Dose (mg) at Each Treatment Area	Cumulative Study Dose
1, 2, 3	Single injection	CCH 0.07 mg	0.3 mL (given as [REDACTED] mL aliquots)	2 doses in Treatment Area 1 and 1 dose in Treatment Area 2	0.14 mg in Treatment Area 1 and 0.07 mg in Treatment Area 2	0.21 mg
4, 5, 6	[REDACTED]	CCH 0.0653 mg	1.4 mL ^a (given as [REDACTED])	2 doses in Treatment Area 1 and 1 dose in Treatment Area 2	0.13 mg in Treatment Area 1 and 0.0653 mg in Treatment Area 2	0.196 mg

^a [REDACTED] mL of the 1.5 mL dilution will be remaining and returned to Endo.

3.5. Determination of Sample Size

As this an exploratory study, no formal sample size calculation is required.

Approximately 10 subjects will be enrolled to receive CCH injection and undergo elective abdominoplasty in this study, with at least 1 subject enrolled in Group 2, Group 3, Group 5, and Group 6, and at least 2 subjects will be enrolled in each of Group 1 and Group 4.

An additional 2 subjects will be enrolled to replace (for overall objective and endpoint analysis purposes) subjects whose abdominoplasty surgeries were delayed due to COVID-19 restrictions.

Completion of 8 subjects with abdominoplasty surgeries completed within the allowable timeframe per protocol (not due to COVID-19 delay) will provide data to meet the primary objective. The 2 subjects whose surgery was delayed due to COVID-19 will not be included for the specific objective but will be analyzed separately.

3.6. Blinding and Randomization

This is an open label, non-randomized study. The pathologist, who is blinded to the dosing schedule will report any observed tissue differences from the control area (not injected).

3.7. Gross Pathology, Histopathology, and Immunohistochemistry

Digital photography will be conducted so that the photographs of the treatment area can assist the histopathologist/evaluator in assessing the gross pathology and histopathology of the excised tissues.

The subjects will be photographed after marking the treatment areas and the injection sites with a surgical marker (but prior to CCH injection) at each dosing visit, while the subject is in a consistent, standardized relaxed standing pose.

At Day 0 (Day of Surgery), the treatment areas will be again photographed after marking the treatment area but prior to the abdominoplasty procedure, while the subject is in a consistent, standardized relaxed standing pose.

No manipulation of the treatment or control areas should be done prior to the photographs being taken.

Histopathology and immunohistochemistry of the excised abdominal tissue will be performed at the central pathology laboratory.

Histopathology and immunohistochemistry findings in the excised abdominal tissues injected with CCH will be compared to histopathology and immunohistochemistry findings in noninjected control tissue. Comparisons will also be made between tissues dosed twice with CCH versus tissue dosed only once, and tissue dosed using the [REDACTED] technique versus the [REDACTED].

3.8. Medical Clearance

Medical clearance for surgery will be obtained at the Screening Visit and also prior to the Surgery Visit (Day -30 through Day -1). Information related to whether or not medical clearance was provided, along with the date of medical clearance will be collected.

3.9. Abdominoplasty Procedure

Following administration of 3 doses of CCH, abdominoplasty and collection of the excised abdominal tissue will occur on Day 0 (Surgery Visit). Information on details of the abdominoplasty surgery along with the date of surgery and whether the tissue excision was performed and shipped will be collected. If abdominoplasty surgery is not performed, or if tissue was not excised, or if the tissue was excised and not shipped, the date and reason for these events will be collected and presented in a listing.

3.10. Medical/Surgical History

Medical and surgical history will be obtained at the Screening Visit and will include previous medications, procedures, surgery, and obstetrics details. Historical and current medical conditions including date of last menstrual period will be recorded. History of tobacco and alcohol use (never, current, former) will also be collected.

Surgical history will include a review of all surgical procedures completed in the prior 5 years and any surgery completed at any time in the treatment areas.

3.11. Prior/Concomitant Medications and Procedures

Any medications taken within the 90 days prior to the Screening Visit or taken from the Screening Visit through the Day 28 Post-surgery follow-up visit/EOS/ET Visit will be recorded.

Any diagnostic, therapeutic, surgical procedure or nondrug therapies (eg, blood transfusions, oxygen supplementation, physical therapy, etc) performed for the above said periods will be recorded.

3.11.1. Prohibited Medications and Procedures

The following medications are prohibited for subjects during the study: anticoagulants (warfarin, heparin, direct thrombin inhibitors, Factor X inhibitors) and antiplatelet agents (aspirin > 150 mg/day and P2Y12 inhibitors, such as clopidogrel), which can cause additional bruising. However, the use of aspirin at a dose level of \leq 150 mg per day will be permitted during study.

The following procedures are not allowed in the abdomen during the course of the study (from the Screening Visit through Day 0):

- Injections (eg, mesotherapy), radiofrequency device treatments, laser treatment, cryolipolysis, or surgery (including subcision and/or powered subcision).
- Any investigational treatment in the abdominal area.
- CoolSculpting® or similar treatments of the abdomen during the 18-month period before injection of study drug.
- Deep massage therapy (such as Endermologie™) or similar therapy, within the abdominal area.
- Creams (eg, Celluvera™, TriLastin®) and/or home therapies within the abdominal area.
- Bath/shower salts or sugar/salt scrubs, lotions, loofahs, or other exfoliating products on the abdominal area.

3.12. Safety Assessments

3.12.1. Adverse Events (AEs)

All AEs occurring after signing the informed consent are to be recorded on the AE pages of the electronic case report form (eCRF). A condition present at baseline that worsens after initiation of study treatment will be captured as an AE; the onset date will be the date the event worsened.

Adverse Events (AEs)

An AE is any unfavorable or unintended change in body structure (signs), body function (symptoms), laboratory result (eg, chemistry, X-ray, etc) or worsening of a preexisting condition associated temporally with the use of the study medication whether or not considered related to the study medication. This would include AEs resulting from concurrent illness, reactions to concurrent medication use, or progression of disease states. AEs include:

- Changes in the general condition of the subject.
- Subjective symptoms offered by or elicited from the subject.
- Objective signs observed by the investigator or other study personnel.
- All concurrent diseases that occur after the start of the study, including any change in severity or frequency of preexisting disease.
- All clinically relevant laboratory abnormalities or physical findings that occur during the study.

Serious Adverse Events (SAEs)

SAEs are those AEs that meet any of the following criteria:

- Results in death
- Life-threatening event

- Results in or prolongs an inpatient hospitalization
- Results in permanent or substantial disability
- Is a congenital anomaly or birth defect
- Any important medical event that may jeopardize the patient or may require medical intervention to prevent one of the outcomes listed above

Adverse Events of Special Interest (AESI)

AEs such as bruising, ecchymosis, hematomas, and contusions that occur remote to the site of drug administration, or any hypersensitivity reactions, including anaphylaxis, will be recorded as an AESI and reported as an AE or SAE as appropriate.

In addition, local AEs associated with the injection site, including bruising, pain, nodules/mass, ulceration, erythema, pruritus, swelling, and/or induration, will be recorded.

Adverse Events Related to Abdominoplasty

As with any surgical procedure, abdominoplasty can also have procedure-related AEs and/or complications. Most common local complications observed include (but are not limited to) seroma, haematoma, infection, skin necrosis, suture extrusions, umbilical anomalies, hypertrophic scars, keloids, poor wound healing, and changes in skin sensation. Systemic complications, though rare, that could be serious and sometimes fatal are deep venous thrombosis and pulmonary thromboembolism, respiratory distress, and even death.

3.12.2. Clinical Safety Laboratory Tests

Laboratory safety testing will be performed as part of the standard of care of the subject's preparation for elective abdominoplasty as deemed required by the investigator at Screening, and prior to surgery on Day 0.

Laboratory safety testing will be performed at the investigative site or designated laboratory. These test results will be assessed for inclusion/exclusion criteria by the investigator. All inclusion/exclusion criteria should be reassessed and verified prior to the first dose of study treatment.

In the event that any safety laboratory testing results are unavailable prior to the subject's first dosing visit, the investigator will notify the sponsor to discuss on a case-by-case basis, prior to administering any study treatment to the subject.

Any clinical post-operative laboratory testing may be performed post-surgery through Day 28 Post-surgery follow-up visit/EOS/ET Visit as deemed necessary by the investigator.

Subjects in Group 1 and Group 4 may undergo additional clinical laboratory safety testing as standard of care (hematology, biochemistry) as part of additional preparation for abdominoplasty surgery.

Clinical laboratory parameters may include, but not be limited to, the following:

- Complete blood count with differential count (CBC W/DIFF).
- Prothrombin time/partial thromboplastin time (PT/PTT).

- Chemistry panel (CHEM PROFILE).
- Human chorionic gonadotropin (B-HCG) qualitative.

Any clinically significant laboratory abnormality observed, will be considered as an AE or SAE as appropriate.

3.12.3. Pregnancy Test

Female subjects of child bearing potential must have a negative serum pregnancy test at the Screening Visit prior to the first dose of study treatment to be enrolled in the study. Female subjects of childbearing potential will undergo a serum pregnancy at the Screening Visit and urine pregnancy tests at each dosing visit, at the Surgery Visit (Day 0) and the Day 28 Post-surgery follow-up visit/EOS/ET Visit.

3.12.4. Vital Signs

Vital sign measurements include systolic and diastolic blood pressure, respiratory rate, pulse rate, body temperature, height, body weight and BMI.

Vital signs (blood pressure, respiratory rate, pulse rate, and body temperature) will be collected on dosing visits up to 2 hours prior to dosing, at 30 minutes after dosing, and 15 minutes after dosing (without body temperature at this time point) on Days -43, -24, -22, -14, -3 and -1. Vital sign measurements will also be collected at Day -30 through Day -1, Surgery Visit (Day 0), Day 7 Post-surgery follow-up visit and, Day 28 Post-surgery follow-up visit/EOS/ET Visit. Pulse and blood pressure should be taken after the subject has been sitting for 5 minutes.

The vital signs of the subject must be stable before the subject can leave direct observation. Height and body weight measurements will be collected at the Screening Visit only, in order to calculate BMI.

Any abnormality in vital sign observed, will be considered as an AE or SAE as appropriate.

3.12.5. 12-Lead Electrocardiogram (ECG)

An ECG will be performed as part of preoperative assessments as per standard-of-care and interpreted by the investigator. The investigator will review the ECG and other preoperative assessment results for clinical significance.

Any ECG result meeting the investigator's or sponsor's criteria for clinical significance will be considered as an AE or SAE as appropriate.

3.12.6. Physical Examination

The complete physical examination will follow the investigative site's standard of care and may include evaluation of the head, eyes, ears, nose, throat, neck (including thyroid), cardiovascular (including assessment of heart, peripheral pulses, presence or absence of edema), lungs, abdomen (including liver and spleen, bowel sounds), lymph nodes, musculoskeletal system (including spine, joints, muscles), neurological system (including cranial nerves, reflexes, sensation, strength), skin, extremities, and other conditions of note.

Complete physical examination (by body system) on each subject will be performed at the Screening Visit, Surgery Visit (prior to surgery), Day 7 Post-surgery follow-up visit, and at the Day 28 Post-surgery follow-up visit/EOS/ET Visit.

3.12.7. Immunogenicity Samples

Serum samples will be collected at the Screening Visit, Surgery Visit Day 0, and Day 28 Post-surgery follow-up visit/EOS/ET Visit for all subjects for the determination of serum anti-AUX-I and anti-AUX-II antibody levels. Neutralizing antibodies will only be tested from anti-drug antibody (ADA) positive samples from the Day 0 and Day 28 visits.

Day 0 samples for anti-AUX-I, anti-AUX-II, and neutralizing antibodies may be collected as part of the standard of care presurgical visit that is nearest to the scheduled date of the abdominoplasty procedure (after dosing visits are completed).

4. STUDY PARAMETERS

4.1. Subject Disposition

Subjects will be considered to have completed the study if they complete the Day 28 Post-surgical follow-up visit. The end of the study is defined as the completion of the final assessment for the last subject enrolled in the trial. Discontinued subjects are those subjects who discontinued the study at any time before the study ends.

For any subject who discontinues the study prematurely, the discontinuation date and reason of early discontinuation will be recorded in eCRF.

Any subject who prematurely withdraws from the study should undergo all ET assessments.

The reason of screen failure will also be recorded in eCRF for subjects who are not enrolled and are considered screen failures.

A subject may be discontinued from the study for the following medical or administrative reasons:

- Withdrawal by subject (reason must be specified).
- An AE.
- Death.
- A protocol violation (reason must be specified, for example: lack of compliance, use of a prohibited concomitant medication, etc).
- The subject was lost to follow-up.
- Other reasons (reason must be specified, for example: the subject moved, pregnancy, investigator decision, sponsor decision to terminate trial, etc).

4.2. Protocol Deviations

Protocol deviations will be identified prior to database lock. Protocol deviations will be derived from the eCRF data and will be obtained from the clinical monitoring reports. All deviations from these sources will be reconciled and duplicate deviations will be removed.

Possible deviations include, but are not restricted to the following deviation types:

- Ineligible subject/study entry criteria not satisfied
- Informed consent not completed correctly
- Prohibited medications/procedure

4.3. Prior/Concomitant Medications

All medications will be coded using the World Health Organization (WHO) Drug Dictionary. The version of the dictionary will be defined in the Data Management Plan (DMP).

A prior medication is any medication taken within 90 days prior to the Screening Visit.

A concomitant medication is defined as any medication taken from the Screening Visit through the Day 28 Post-surgery follow-up visit/EOS/ET Visit or the medication is reported as ongoing.

4.4. Safety Parameters

4.4.1. Adverse Events

AE verbatim terms as reported by the investigator will be mapped to system organ class (SOC) and preferred term (PT) using the Medical Dictionary for Regulatory Activities (MedDRA). The MedDRA version to be used in this study will be defined in the DMP.

4.4.1.1. Treatment-Emergent Adverse Events (TEAEs)

A TEAE is any condition that was not present prior to treatment with study medication but appeared following treatment, was present at treatment initiation but worsened during treatment, or was present at treatment initiation but resolved and then reappeared while the individual was on treatment (regardless of the intensity of the AE when the treatment was initiated).

The following rules will apply in cases where the start date of an AE is known:

- If the AE onset date is prior to first injection, then the AE will not be considered a TEAE.
- If the AE onset date is equal to or later than first injection, then the AE will be considered a TEAE.

Refer to Section 6.3.1.1 to identify TEAE status when start date of an AE is unknown.

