Marking and labeling the site of injection (treatment and control) with surgical marker (Treatment Area 1, Non-injected Control Area, and Treatment Area 2)	X	X	X	X	X	X	X
Digital Photography ⁱ	X	X	X	X	X	X	X
CCH injection (approximately 0.07 mg) at Area 1	X	X	X	X	X	X	X
CCH injection (approximately 0.07 mg) at Area 2							
Abdominoplasty procedure							
Tissue excision and handling procedures for shipment							
Injection site evaluation (ie, adverse reactions/local tolerability in treatment areas) ^k	X	X	X	X	X	X	X
All other adverse events	X						Monitored Throughout Study

Note: AUX-I= Clostridial class I collagenase, AUX-II=Clostridial class II collagenase, ECG= Electrocardiogram, EOS= End of Study

Note: Unless otherwise stated above or outlined below (and with the exception of injection site reactions/local tolerability in the area treated), all assessments should be completed prior to study treatment administration on Treatment Days.

^a Performed prior to any study-required assessments.

^b Laboratory safety testing will be performed at the investigative site or designated laboratory, as part of the standard of care (hematology, biochemistry, ECG, etc) of the subject's preparation for elective abdominoplasty as deemed required by the investigator. These testing results will be assessed for inclusion/exclusion criteria by the investigator. All inclusion/exclusion criteria should be reassessed and verified prior to the first dose of study treatment. In the event that any safety laboratory testing results are unavailable prior to the subject's first dosing visit, the investigator will notify the sponsor to discuss on a case-by-case basis, prior to administer treatment to the subject.

^c Physical examination performed prior to surgery.

^d Vital signs (blood pressure, respiratory rate, pulse rate, and body temperature) will be collected up to **2 hours prior** to dosing, at **30 minutes after dosing**, and also at **15 minutes after dosing (without body temperature)** on Days -43, -24, -22, -14, -3 and -1 at dosing visits. All vital sign measurements should be taken after the subject has been sitting for 5 minutes. Vital signs **must be stable** before the subject is discharged.

^e Any clinical post-operative laboratory testing may be performed post-surgery through Day 28 as deemed necessary by the investigator.

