6.3.1. Imputation of Partial Dates

6.3.1.1. TEAE Status When Start Date and Time Is Unknown

The following rules will apply in cases where start date of an AE is unknown:

- If the AE onset date and time is unknown and the end date and time is after the date and time of the first dosing date or ongoing, then the AE will be considered a TEAE.
- If the AE onset date and time is unknown and the end date and time is before the date and time of the first dosing date, then the AE will not be considered a TEAE.
- If both the start date and time and end date and time are unknown (or ongoing), then the AE will be considered a TEAE, following the worst-case principle.

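### The known-start TEAE rule in SAP 4.4.1.1 compares onset by date only, so an event that begins on the first dosing day but before the injection is flagged as treatment-emergent

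*SAP*

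**What the plan says.** SAP 4.4.1.1 first defines a TEAE in words. The leading limb is "any condition that was not present prior to treatment with study medication but appeared following treatment". Two further limbs cover conditions already present when treatment began that then worsened, or that resolved and came back on treatment.

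The section then gives two working rules for events with a known start. The first is "If the AE onset date is prior to first injection, then the AE will not be considered a TEAE". The second is "If the AE onset date is equal to or later than first injection, then the AE will be considered a TEAE". Neither mentions a time of day.

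For unknown starts the section refers to SAP 6.3.1.1, which works at a finer resolution. The rule that opens "If the AE onset date and time is unknown and the end date and time is before the date and time of the first dosing" classes the event as not a TEAE. If the event ended after the first dose, is ongoing, or has no known end either, it is a TEAE. For the last of these cases the SAP cites its worst-case principle.

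Other relevant text:
- AEs are recorded from consent (SAP 3.12.1).
- On dosing days, apart from injection-site evaluation and unless otherwise specified, "all assessments should be completed prior to study treatment administration on Treatment Days" (note to SAP Table 1).
- Pre-dose vital signs may be taken up to 2 hours before dosing, and "Any abnormality in vital sign observed, will be considered as an AE or SAE as appropriate" (SAP 3.12.4).
- The listing of CCH administration shows start and end date and time (SAP 7.9.1).
- TEAEs are an endpoint under the secondary safety objective (Protocol Section 3).

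**The concern.** The working rule does not carry out the definition it follows. An event that starts and ends on the first dosing morning, before any CCH is given, meets none of the three limbs, yet the date rule makes it a TEAE. An event that starts that morning and continues unchanged is also flagged, although it was present before treatment and neither worsened nor recurred.

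The two sections also disagree in an awkward direction. For an event that is over before the injection, a known start leads to TEAE and an unknown start leads to non-TEAE, so the better-documented event gets the wrong label. The worst-case principle cannot justify this where both times are on record, because nothing is then missing.

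At stake is the correctness of a flag that defines a named secondary endpoint, in a study with 1 or 2 planned subjects per group whose results are reported through listings and narratives.

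**Working it through.** The documents give no figure to reproduce, so the check applies the rules to test events.

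Rules as written:
- Known start (SAP 4.4.1.1): TEAE if onset date ≥ date of first injection, otherwise not.
- Definition (SAP 4.4.1.1): for a new event that neither worsens nor recurs, TEAE only if onset date and time ≥ date and time of first injection.
- Unknown start (SAP 6.3.1.1): not a TEAE if the end date and time is before the first dose. TEAE if it ended after the first dose, is ongoing, or has no known end.

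Assume a first injection at 10:00 (an illustrative time, not from the documents) and take four events:

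| Event | Known-start date rule | Definition, using date and time | SAP 6.3.1.1, had the start been unknown |
|---|---|---|---|
| A. Onset the evening before, found pre-dose, ongoing | Not TEAE | Not TEAE | TEAE (worst case) |
| B. Onset 09:00 on the dosing day, ongoing | TEAE | Not TEAE | TEAE (worst case) |
| C. Onset 09:00, ended 09:40 on the dosing day | TEAE | Not TEAE | Not TEAE |
| D. Onset 10:15 on the dosing day | TEAE | TEAE | TEAE |

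Reading across the rows:
- In A the date rule and the definition agree. What matters is when the event began, not when it was found. The last column differs only because a missing start is resolved to the worst case.
- In B and C the date rule contradicts the definition.
- In C the date rule also contradicts SAP 6.3.1.1. Knowing the start turns a wholly pre-dose event into a TEAE.
- D is a TEAE under every rule.

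Replacing the date comparison with a date-and-time comparison changes B and C to not TEAE and leaves A and D as they were. Only same-day, pre-injection onsets change class, which means one calendar day per subject.

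How such an event can arise: AEs are recorded from consent, and pre-dose assessments take place on the dosing day. An onset that morning can therefore be recorded for a subject who is then injected.

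**The case against.** Several arguments against the point have force.

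*The vital-sign route is narrow.* A reader might infer from SAP 3.12.4 that pre-dose vital signs will regularly generate such events. The documents do not support that:
- Protocol 8.1.4 makes a vital sign an AE only if it meets the investigator's or sponsor's criteria for clinical significance.
- Clinically significant vital-sign abnormalities fall under exclusion 2e, although that item names screening and pre-surgery preparation rather than the dosing visit.
- Criteria are re-verified before the first dose (Schedule of Activities, footnote b), and a subject who fails them at the first dosing visit is a screen failure (Protocol 5.4). Such a subject would not be injected and would not enter the Safety Population.

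What remains is a minor event, such as a headache, that starts that morning in a subject who is still dosed. The documents also give no reason to expect AEs from marking the sites.

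*No TEAE percentage is planned.* A reader might reason that one subject in about 10 is 10 percentage points. SAP 7.9.2 names AE listings only, with no TEAE table or listing, and Protocol 9.3.2.1 summarises AEs rather than TEAEs. The figure attaches to no named output. Even if a TEAE proportion were produced, a subject with any later TEAE would already be counted.

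*The flag is not a causality call.* A reader might take the flag to attribute a pre-dose event to CCH. The investigator assesses relatedness separately (SAP 4.4.1.3) and can record such an event as not related.

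*The date rule may be deliberate.* SAP Table 5 derives AE duration and AE onset day from dates alone, and no text seen here states that the AE form records onset time. If it does not, sending same-day events to TEAE follows the worst-case principle the SAP uses elsewhere. This stands as a condition on the fix. It does not remove the inconsistency, because the SAP does not describe the rule as a default, and without AE times the comparison in SAP 6.3.1.1 could not be carried out as written.

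*The wording could be read more generously.* The rule refers to first injection rather than its date, so a date-and-time reading is possible. It is the less natural one, because the variable compared is an onset date.

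**Conclusion.** The point holds as an inconsistency in the text. As written, SAP 4.4.1.1 classes an event with onset on the first dosing day, before the first injection, as a TEAE. Its own definition does not, and SAP 6.3.1.1 would not if the event had ended before the injection and its start were unknown.

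It does not extend to events merely found before the injection. One that began on an earlier day is already classed as not a TEAE.

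The size is small: one calendar day per subject, about 10 enrolled subjects, minor events only, no hypothesis tests and no named TEAE summary. No percentage-point shift should be claimed. It remains worth correcting because TEAEs are a named secondary endpoint and the change is trivial.

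The conclusion assumes that the rule is programmed on dates as worded. The benefit of a time-based rule also assumes that AE onset time is collected. SAP 6.3.1.1 implies this and Table 5 does not confirm it. The eCRF and the SAP Module 2 shells were not available to settle it.

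**What to change.** First check whether the AE form records onset time.

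If it does, replace the two known-start bullets in SAP 4.4.1.1 with a date-and-time rule:
- Onset before the start date and time of the first injection: not a TEAE.
- Onset at or after it: TEAE.
- Onset on the day of first injection with the time missing: TEAE, under the worst-case principle.

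The limbs for worsening and for recurrence on treatment stay as they are.

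If onset time is not collected, keep the date rule, state in SAP 4.4.1.1 that it is a conservative default for same-day events, and align SAP 6.3.1.1 with it by removing the time comparison.

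The cost is a line or so of SAP text and one line of code. Injection start times are already due to be listed under SAP 7.9.1, so no new exposure data are needed. The change is best made before database lock.
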